### 2.2.2 Secondary Safety Endpoints

The secondary Safety endpoints of the study are:

In **Arm 1 and Arm 3 (PTPs)**, the secondary safety endpoints are:

- Incidence of inhibitor formation to FVIII in at least 200 PTPs after 10 EDs and after 50 EDs with rVIII-SingleChain.
- Percentage of PTPs who develop antibodies against rVIII-SingleChain.
- Percentage of PTPs who develop antibodies to CHO proteins.

In **Arm 2 (PUPs)**, the secondary safety endpoints are:

- Incidence of high-titer inhibitor formation to FVIII after 10 EDs with rVIII-SingleChain in at least 50 PUPs.
  - A positive inhibitor is defined as two consecutive positive results ( $\geq 0.6$  Bethesda units (BU) /mL from the central lab.
  - The high-titer inhibitor is defined as any inhibitor tier of  $\geq 5$  BU/mL) during the study.
- Incidence of low-titer inhibitor formation (FVIII after 10 EDs and after 50 EDs with rVIII-SingleChain in at least 50 PUPs.

- The low-titer inhibitor is defined as any inhibitor tier of  $\geq 0.6$  and  $< 5$  BU/mL) during the study.
- Incidence of total (low- and high-titer) inhibitor formation to FVIII after 10 EDs and after 50 EDs with rVIII-SingleChain in at least 50 PUPs.
- Incidence of transient inhibitors (negative results within 6 months after diagnosis)
- Percentage of PUPs who develop antibodies against rVIII-SingleChain.
- Percentage of PUPs who develop antibodies to CHO proteins.
- Percentage of PUPs with clinically significant abnormal values for blood pressure, or heart rate, or body temperature at 1, 2, 3, or 6 hours after the first rVIII-SingleChain injection.
- Percentage of PUPs with treatment-emergent clinically significant abnormal values for blood pressure, heart rate, or body temperature during the course of the study.

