Inhibitors are typically classified as either high- or low-responding, depending on how an individual's immune system is stimulated following repeated exposures to FVIII. High-responding inhibitors can rise quickly to very high levels (Bethesda titer ≥ 5 units) if the immune system reacts briskly or strongly to repeated exposure to FVIII. In high-titer inhibitors without continued exposure (a period of months or years), the titer level could decrease to a low level. Low-responding inhibitors demonstrate a slower or weaker responding immune system and the Bethesda titer will remain low (Bethesda titer < 5 units). However, the characteristics of an inhibitor can change over time. Low-titer inhibitors may also disappear spontaneously within several weeks or months, achieving immune tolerance in patients [[DiMichele, 2008](#)].

“The union of Factor VIII with its inhibitor is not associated with allergic reactions. The presence of an inhibitor does not change the typical site, frequency, or severity of bleeding, however the inhibitor makes control of hemorrhages more difficult.” [Kasper, 2004].

Inhibitor development usually occurs between a median age of 1.7 and 3.3 years regardless of the replacement factor product used, and occurs less frequently after the age of 5 years. Inhibitors are generally detected between a mean of 9 and 21 exposure days (EDs) with a median of 12 EDs following exposure to factor replacement products. Inhibitor development is most commonly detected within the first 50 EDs, and new inhibitors are rarely detected after 200 treatment days with the replacement factor [DiMichele, 2002].

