8.6.1 Blood Samples for Inhibitors and Antibodies

The presence of inhibitors to FVIII, antibodies against rVIII-SingleChain, and antibodies against CHO proteins will be analyzed by the central laboratory. For the inhibitor blood samples, subjects should have a 4-day washout from last FVIII infusion before blood draw if possible.

1. In **Arms 1 and 3 (PTPs)**, blood samples for inhibitors to FVIII, antibodies to rVIII-SingleChain, and antibodies to CHO proteins will be collected at the closest visits after 10 EDs, after 50 EDs, and after 100 EDs as outlined in [Table 8](#).
2. In **Arm 2 (PUPs)**, blood samples for inhibitors to FVIII, antibodies against rVIII-SingleChain, and antibodies to CHO proteins will be collected at all scheduled visits.

Blood samples drawn for inhibitor assessment should be sent to the central laboratory for testing with the Nijmegen assay. A subject will be considered to have developed an inhibitor if the titer result is ≥ 0.6 BU/mL and verified by repeat testing. FVIII inhibitors will be further categorized as low-titer (≤ 5 BU/mL) and high-titer (> 5 BU/mL). If an inhibitor is suspected, all inhibitor testing must be expedited and a repeat sample obtained as soon as possible to confirm results.

Details regarding sample collection, handling, deep freezing of samples and shipment to the central laboratory are given in the Laboratory Manual in the Investigator Site File.

If an inhibitor is suspected (eg, lack of efficacy of IMP), additional visits may be scheduled for inhibitor assessment. If a subject undergoes surgery, blood samples will be collected at least 28 days after surgery to test for inhibitors to FVIII, antibodies against rVIII-SingleChain, and antibodies against CHO proteins in all study arms. In addition, a pre-surgery blood sample for inhibitor testing is recommended for PUPs in Arm 2.

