11.3.3.4 Secondary Safety Analysis

11.3.3.4.1 Incidence of Inhibitor Formation to FVIII at Intermediate Timepoints of Exposure to rVIII-SingleChain

Arms 1 and 3 (PTPs)

To calculate the inhibitor incidence after 10 EDs (after 50 EDs, and after 100 EDs), the numerator will include all subjects with inhibitors observed at the closest visit up to 10 EDs (≤ 10 EDs) (up to 50 EDs, and up to 100 EDs). The denominator will include all subjects with at least 10 EDs (≥ 10 EDs) (at least 50 EDs, and at least 100 EDs) plus subjects with less than 10 EDs (< 10 EDs) (less than 50 EDs, and less than 100 EDs) but with inhibitors.

Arm 2 (PUPs)

Inhibitor incidence in PUPs will be analyzed analogously to PTPs. The same principles will be applied, taking into account: number of subjects at risk for the relevant number of EDs (after 10 EDs and after 50 EDs) and inhibitor type (low, low + high).

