#### 4.7.1 Incidence of Inhibitor Formation

The incidence of inhibitor formation to FVIII will be estimated for subjects in the Safety population who did not have inhibitors at baseline. Baseline assessments are defined as those assessments done before date and time or on the same date and time of the first dose. If time of inhibitors assessment or time of first dose is missing then the inhibitor result taken at the same date of the first dose will be considered as baseline. Inhibitor formation will be defined as any post-baseline inhibitor titer  $\geq 0.6$  BU/mL identified and confirmed by re-testing at a subsequent visit. Both tests must be performed by a central laboratory. A positive result not confirmed as positive by re-testing at a subsequent visit result will be considered as non positive. In the KM analysis of inhibitor occurrence, the first positive result will be considered as an event. A positive result not confirmed as positive by re-testing at a subsequent visit result will not be considered as an event. Positive FVIII inhibitors will be further categorized as low or high titer. Low-titer inhibitors are defined as positive inhibitors with a titer of  $\leq 5$  BU/mL. High-titer inhibitors are defined as positive inhibitors with a titer of  $> 5$  BU/mL.

For the inhibitor incidence after 10 Total EDs, the numerator will include all subjects with inhibitors observed at the closest visit up to 10 EDs ( $\leq 10$  EDs). The denominator will include all subjects with at least 10 EDs ( $\geq 10$  EDs) plus subjects with less than 10 EDs but with inhibitors.

- Numerators = Number of PTP subjects who develop inhibitors up to 10 EDs ( $\leq 10$  EDs)
- Denominators = Total number of PTPs with at least 10 EDs ( $\geq 10$  EDs) + subjects with less than 10 EDs with inhibitors. Subjects not tested at  $\leq 10$  EDs will be excluded.

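### SAP 2.2.2 lets one PUP count as both low-titer and high-titer, so low-titer incidence can be overstated and low plus high can exceed total

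*SAP*

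**What the plan says.** **SAP 2.2.2 (Arm 2).** "A positive inhibitor is defined as two consecutive positive results" of at least 0.6 BU/mL from the central laboratory. Two class rules follow. "The high-titer inhibitor is defined as any inhibitor tier of" 5 BU/mL or more, and "The low-titer inhibitor is defined as any inhibitor tier of" at least 0.6 and below 5 BU/mL. Both look across the whole study. The endpoints they serve are high-titer incidence after 10 EDs, and low-titer and total incidence after 10 and after 50 EDs.

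**SAP 4.7.1.** "Positive FVIII inhibitors will be further categorized as low or high titer". It continues: "Low-titer inhibitors are defined as positive inhibitors with a titer of" 5 BU/mL or less, with high titer above 5. Numerators count inhibitors that develop up to the stated number of EDs. The algorithm is written for PTPs and carried over to PUPs.

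**Protocol 8.6.1.** "FVIII inhibitors will be further categorized as low-titer (≤ 5 BU/mL) and high-titer (> 5 BU/mL").

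**Protocol 11.3.3.4.** The PUP analysis is by "inhibitor type (low, low + high").

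**Other uses of the two classes.** Protocol 11.3.5.3 asks for separate low-titer, high-titer and overall summaries, and SAP 4.5.1 summarizes EDs by high or low titer level.

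**Protocol 1.1.** It warns that "the characteristics of an inhibitor can change over time", and that a high titer can come down to a low level.

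**The concern.** Each class rule in SAP 2.2.2 asks only whether a reading of that kind exists. Neither says that meeting one rules out the other, and the two confirming results need not fall in the same class. The sections that speak of two categories do not say whether the first, the peak or any titer decides. A programmer looking for a subject-level rule finds it only in 2.2.2, and that rule allows overlap.

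Overlap is plausible. Protocol 1.1 describes titers that move, PUPs are sampled at every scheduled visit (protocol 8.6.1), and each positive result must be repeated (protocol 8.6). Low-titer incidence after 10 and after 50 EDs is a named secondary safety endpoint. If boys with high-titer inhibitors also enter its numerator, the printed low-titer figure no longer describes boys whose inhibitor stayed low.

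**Working it through.** **1. No planned figure to reproduce.** The documents give no expected low-titer incidence, and protocol 11.1 and SAP 3.9 state that no sample size calculation was done.

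**2. Apply the rules to example titer series.** All are invented, all meet the confirmation rule, and the cut is taken as in SAP 2.2.2.

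| Series (BU/mL) | Literal low? | Literal high? | Class by peak | Class by first titer |
|---|---|---|---|---|
| 1.2, 8.0 | yes | yes | high | low |
| 8, 12, 3, 1 | yes | yes | high | high |
| 20, 30 | no | yes | high | high |
| 0.9, 1.5 | yes | no | low | low |

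The two series that cross 5 BU/mL fall in both classes under the literal rule. The series 1.2, 8.0 also changes class between a first-titer and a peak reading of SAP 4.7.1, so the missing rule matters.

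**3. The ED window.** A rise such as 1.2 to 8.0 can occur wholly inside 10 or 50 EDs. A later fall affects those endpoints only if the window fixes when the inhibitor develops while the class is set by any reading in the study. SAP 2.2.2 and 4.7.1 together permit that reading but do not settle it.

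**4. Size, as an illustration.** Inputs:
- N = 24 PUPs, all taken as evaluable (protocol 11.1; SAP 3.9 under sample size estimation, although other SAP text still says 50).
- Background inhibitor incidence within 50 EDs is 35.4% (protocol 1.1). 24 × 0.354 = 8.5, taken as 8.
- h = number of the 8 who are high-titer. The documents do not give it; assumed 4 to 6.
- k = number of those h boys with a recorded reading from 0.6 to below 5. Unknown; any value from 0 to h.

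Formulas:
- exclusive low = 8 − h
- literal low = 8 − h + k
- excess = k/24
- literal low + high = 8 + k, against a total of 8

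Intervals are exact Clopper-Pearson 95%, the method in SAP 4.7.1.

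| h | Exclusive low | Literal low, k = h | Excess over k = 0 to h | Low + high (total 8) |
|---|---|---|---|---|
| 4 | 4/24 = 16.7% (4.7 to 37.4) | 8/24 = 33.3% (15.6 to 55.3) | 0 to 16.7 points | 8 to 12 |
| 5 | 3/24 = 12.5% (2.7 to 32.4) | 8/24 = 33.3% (15.6 to 55.3) | 0 to 20.8 points | 8 to 13 |
| 6 | 2/24 = 8.3% (1.0 to 27.0) | 8/24 = 33.3% (15.6 to 55.3) | 0 to 25.0 points | 8 to 14 |

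An intermediate case, h = 4 and k = 2, gives 6/24 = 25.0% (9.8 to 46.7) and a sum of 10. Each double-counted boy adds 1/24 = 4.2 points.

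**The case against.** The best reply is that SAP 2.2.2 is an endpoint list, and that the analysis text intends a partition. SAP 4.7.1 and protocol 8.6.1 place inhibitors in one of two categories, protocol 11.3.3.4 pairs low with low plus high, and SAP 4.5.1 uses titer level as a grouping. The analysis is descriptive. High-titer and total counts are reported in their own right, so low-only can be recovered by subtraction. Parts of SAP 4.7.1 are redacted and the table shells are a separate document, so an assignment rule may exist where it cannot be seen.

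Much of this stands, and it rules out several stronger readings that a reader might infer:

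- *That high-titer boys are counted as low-titer and the incidence is overstated.* Double counting is the literal reading of 2.2.2. Given the two-category wording elsewhere, it is not certain.
- *That nearly every high-titer boy will be counted twice.* No figure supports this. Follow-up does not always run until the titer is below 0.6 BU/mL: a PUP with a confirmed high titer who declines the substudy is withdrawn (protocol 4.2.1), inhibitor treatment is capped at 24 months (protocol 3.3), and protocol 8.10.6 allows the study to end for the subject at that point.
- *That the severity mix is lost.* Total minus high still gives low-only, provided subject counts over the same period are subtracted.

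What does not stand is that the two-category wording settles the matter. It shows what was probably intended but gives no rule. SAP 3.5.6 separates a time-varying inhibitor status from a group fixed for each subject when dividing positive from negative; nothing comparable is written for low and high.

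**Conclusion.** The point holds as a gap in the definitions. As written, SAP 2.2.2 allows one subject to be both low- and high-titer, and no visible text says which titer decides. Relative to a rule with one class per subject that keeps the high-titer definition, any double counting can only raise low-titer incidence. The excess is 0 to 25 percentage points on the assumptions used: 24 evaluable PUPs, 8 inhibitors, and 4 to 6 of them high-titer. The upper end requires all 6 high-titer boys to have a recorded reading in the low range, and the true excess may be zero. Total incidence does not change if each boy is counted once, and high-titer incidence does not change under its any-reading rule. The plan should be corrected because the endpoint is named and the arm is small enough for one boy to move the estimate by 4.2 points.

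**What to change.** In SAP 2.2.2, leave the high-titer rule as it is. Define low-titer as a confirmed inhibitor with no central-laboratory titer that meets the high-titer cut over the same period used for the high-titer endpoint. Repeat this in SAP 4.7.1, and state that each subject has one class and that low plus high equals total, in subject counts, at each exposure point.

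If the sponsor prefers peak titer within each ED window, apply it to both classes and state that the 10-ED high-titer count may fall. For example, a boy at 3 BU/mL on ED 8 and 12 BU/mL on ED 20 developed his inhibitor by 10 EDs and is high-titer under the whole-study rule, but would be low-titer at 10 EDs under a window rule.

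Separately, reconcile the boundary. A titer of exactly 5 BU/mL is high in SAP 2.2.2 and in the protocol 2.1.2 endpoint, but low in SAP 4.7.1 and protocol 8.6.1. This write-up takes no position on which is right.

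The cost is about one sentence of SAP wording, with no new data and no change to how subjects are treated. Under the main fix, the low-titer count stays the same or falls, and the high-titer and total counts do not move.

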### 2.3 Other Endpoints

CCI

## 3 Study Design

### 3.1 Discussion of Study Design

This multicenter, non-randomized, open-label, multiple-arm phase 3 extension study will continue to investigate the safety and efficacy of rVIII-SingleChain in PTPs and PUPs with severe hemophilia A. This study will evaluate the prophylaxis and on-demand treatment of bleeding episodes in at least 200 PTPs who achieve at least 100 EDs as well as in at least 50 PUPs. In Arms 1 and 3 (PTPs), each PTP will stay in this study until they have achieved at least 100 EDs, which overall is expected to take up to 5 years. In Arm 2 (PUPs), each PUP will stay in this study until they have achieved at least 75EDs, which overall is expected to take up to 5 years. A surgical substudy (open to subjects from all study arms) will investigate the use of rVIII-SingleChain in surgery. CCI

[Valentino et al., 2015].

Eligible subjects will be enrolled in 3 Arms, as detailed in [Section 2](#).

This study is designed to collect data on the use of rVIII-SingleChain to assess long-term safety and efficacy beyond the outcome from pre-marketing authorization clinical studies as well as to assess inhibitor development and characterize efficacy and safety of rVIII-SingleChain in PUPs. Inhibitor development is of particular interest for the safety of rVIII-SingleChain.

The preceding lead-in clinical studies, i.e. CSL627\_1001 and CSL627\_3002, are referred to as pivotal studies.

### 3.2 Study Treatment Dosing Regimen

In all study arms, the investigator will assign subjects to either prophylaxis or on-demand treatment regimens with rVIII-SingleChain. All subjects will be dosed according to the actual potency printed on the vial label and will be treated by IV injection. On-demand and prophylaxis doses can be adjusted as necessary at the discretion of the investigator. In all study arms, changes in treatment regimens (on-demand or prophylaxis) and dose modifications are allowed and are permitted at the investigator's discretion.

#### 3.2.1 Prophylaxis Treatment Regimen

In previous studies, most subjects received prophylaxis treatment with an initial range of 15 to 50 IU/kg rVIII SingleChain every second day or 2 to 3 times per week.

- In Arm 1 and Arm 3 (PTPs), the investigator will determine the rVIII-SingleChain prophylaxis dose and dosing schedule for the subject based upon the subject's pharmacokinetic (PK) profile, rVIII-SingleChain PK data, previous FVIII treatment regimen, bleeding phenotype (if available), and taking into consideration the World Federation of Hemophilia (WFH) guidelines [[WFH, 2012](#)].
- In Arm 2 (PUPs), the investigator will determine the rVIII-SingleChain prophylaxis dose and dosing schedule at their discretion, taking into consideration the WFH guidelines [[WFH, 2012](#)], subject's age and other disease characteristics (e.g. bleeding phenotype).

### 3.2.2 On-demand Treatment Regimen

Subjects assigned to the on-demand treatment regimen will treat themselves or be treated by a caregiver/guardian as needed for any bleeding episode. For the on-demand treatment of bleeding episodes, the initial treatment dose and subsequent dose(s) to achieve hemostasis will be recorded, as well as confirmation that the subject received product and was given instruction for proper use.

After each bleeding episode, the number of injections required to achieve hemostatic efficacy with rVIII-SingleChain will be documented by the subject/caregiver/guardian. The details of each bleeding episode (e.g., type, location, and severity), treatment dose per event, and time required for improvement/resolution of symptoms will be recorded.

### 3.2.3 Treatment Regimen for Bleeding Episodes

In the event of a bleeding episode, subjects will be treated at a dose pre-determined by the investigator based on the type and severity of the bleeding episode. All subjects should treat bleeding episodes with rVIII-SingleChain when they occur, regardless of the assigned treatment regimen. The desired FVIII level for the treatment of a bleeding episode (on-demand treatment) is based on the recommendations of the WFH [[WFH, 2012](#)].

### 3.2.4 Surgery Doses

In all study arms, the investigator will determine the rVIII-SingleChain dose and treatment schedule for a subject who is scheduled for surgery based on the type of surgery and the clinical status of the subject. The PK data of the study subject or population (if available) will be utilized for calculating the dose regimen of rVIII-SingleChain before, during and after surgery to achieve and maintain the FVIII activity level recommended by the WFH guidelines [[WFH, 2012](#)].

### 3.2.5 Preventive and Additional Doses

In all study arms, preventive doses of rVIII-SingleChain are allowed. A preventive dose is defined as a dose that is taken prior to an activity or a minor procedure to prevent or minimize a bleeding episode.

In all study arms, additional doses of rVIII-SingleChain are allowed. An additional dose is defined as a dose that is taken beyond the need to control hemostasis and does not contribute to the efficacy evaluation of the bleeding episode.

These preventive and additional doses should be captured in the subject's electronic diary (eDiary) or electronic case report form (eCRF), if administered in the hospital. They will not contribute to the haemostatic efficacy evaluation for the bleeding episode, but will contribute to EDs and consumption data.

### 3.2.6 Change in Treatment Regimens and Dose Modifications

In all study arms, changes in treatment regimens (on-demand or prophylaxis) and dose modifications are allowed and will be permitted at the investigator's discretion. The timing of dose adjustment should be flexible and based on the type of bleeding episode, the location of the bleeding episode, the age of the subject, and bleeding phenotype.

3.2.7 CCI [Redacted]

3.2.7.1 CCI [Redacted]

CCI [Redacted]

3.2.7.2 CCI [Redacted]

CCI [Redacted]

3.2.7.3 CCI [Redacted]

CCI [Redacted]

3.2.7.4 CCI [Redacted]

CCI [Redacted]

3.2.7.5 CCI [Redacted]

CCI [Redacted]

### 3.3 Study Schedule

The schedule of assessments can be found in the CSP.

### 3.4 Concomitant Medication Information

Medications other than rVIII-SingleChain taken by a subject at enrollment and continues to be taken during the study are regarded as concomitant medication and must be documented in the eCRF.

The following therapy is permitted during the study:

- Blood product transfusion (whole blood, erythrocytes [red blood cells], or platelets) may be used as clinically indicated.
- Plasma and cryoprecipitate should be used only when clinically indicated and not as a substitute for FVIII, unless FVIII is unavailable and as a rescue medication.
- Other marketed FVIII products should be used as rescue medication only when there is poor/no response to rVIII-SingleChain or when rVIII-SingleChain is not available.

Medications known to have an effect on blood clotting are to be used with caution.

CCI

### 3.5 Study Populations

Unless specify otherwise, all analyses in all study populations will be performed separately for PTPs and PUPs.

#### 3.5.1 Enrolled Population

The Enrolled population will comprise all subjects who provided informed consent and were not screen failures.

#### 3.5.2 Safety Population

The Safety population will consist of all Enrolled population subjects who received at least one dose of rVIII-SingleChain during the study for any reason (e.g., surgery, routine prophylaxis, on-demand treatment).

